***ADA response endpoints:***

- An **ADA positive patient** is defined as a patient with at least one treatment-induced or treatment-boosted ADA positive sample at any time during the on-study observation period
- ADA incidence** is defined as the number of ADA positive patients among evaluable patients divided by the number of evaluable patients.

- **ADA prevalence** is defined as the sum of the number of patients with preexisting ADA and the number of patients with treatment induced ADAs, divided by the number of evaluable patients

### **2.1.8 Pharmacodynamic/genomics endpoints**

Not applicable.

### **2.1.9 Quality-of-life endpoints**

Not applicable.

### **2.1.10 Health economic endpoints**

Not applicable.

### **2.1.11 Exploratory endpoints**

Exploratory endpoints are FISH, MRD, immune genetic determinants, immune phenotyping bone marrow/blood, and soluble CD38.

### **2.1.12 Further therapy after discontinuation of investigational medicinal product administration during the study**

Further therapies after discontinuation of IMP will be assessed.

## **2.2 DISPOSITION OF PATIENTS**

This section describes patient disposition for both patient study status and the patient analysis populations.

Screened patients are defined as any patients who signed the informed consent. A listing of screening failure patients (screened patients who were not treated with isatuximab) and reason for screening failure will be provided.

The number and percentage (when applicable) of patients in each of the following analysis population will be provided:

- All treated/safety population
- DLT evaluable population
- Pharmacokinetics population
- ADA evaluable population

For all above categories (except for the all treated population) percentages will be calculated using the number of patients in the all treated population. For the all treated population, no percentages will be calculated.

For patient study status, the number and percentage of patients in each of the following categories will be provided using the all treated/safety population:

- Patients off treatment and reasons for treatment discontinuation
- Patients on treatment at time of the analysis cut-off date

Major deviation potentially impacting efficacy/safety analyses include:

- No prior treatment with IMiD and PI (for 2 cycles or 2 months of treatment)
- Was not refractory to the most recently received both IMiD and PI included therapy
- Did not achieve an MR or better to all prior lines of therapy.

All critical or major deviations will be summarized in a table giving numbers and percentages of patients with deviations. Protocol deviation will also be listed.

### **2.2.1 Randomization and drug dispensing irregularities**

Not applicable, as this is a non-randomized study.

## **2.3 ANALYSIS POPULATIONS**

### **2.3.1 All treated/safety populations**

The all treated/safety population will include all patients who have given their informed consent and who have received at least one dose (even incomplete) of isatuximab.

This population is the primary population for the analyses of efficacy and safety parameters. All analyses using this population will be based on the treatment actually received.

### **2.3.2 DLT evaluable population**

The DLT evaluable population is the subset of patients from the all treated population who have completed the first cycle which consists of 4 administrations of the IMP, or they discontinued the IMP before completion of the first cycle for a DLT. In practice, a “Dose-Limiting Toxicities” form should have been filled in at the end of Cycle 1. If there are missing or incomplete data that influence the evaluation of DLT the patient will not be evaluable for DLT. Patients excluded from this population will be replaced.

### **2.3.3 Pharmacokinetic population**

The PK parameter analysis will be performed on the all treated/safety population who have a concentration data.

### 2.3.4 ADA population

The ADA evaluable population will include all treated patients with at least one ADA assessment with a reportable during the ADA on-study observation periods.

## 2.4 STATISTICAL METHODS

### 2.4.1 Demographics and baseline characteristics

Continuous data will be summarized using the number of available data, mean, standard deviation, median, minimum, and maximum for each treatment group. Categorical and ordinal data will be summarized using the number and percentage of patients in each dose level cohort.

Parameters described in [Section 2.1.1](#) will be summarized by dose level cohort and overall group using descriptive statistics.

Past medical or surgical history other than multiple myeloma will be summarized by SOC (sorted by internationally agreed order) and PT (sorted by descending frequency in overall group and alphabetical order) for the all treated population.

### 2.4.2 Prior or concomitant medications (other than anticancer therapies)

Prior and concomitant medications will be presented for the all treated population.

Medications will be summarized according to the WHO-DD dictionary, considering the first digit of the anatomical therapeutic chemical (ATC) class (anatomical category) and the first 3 digits of the ATC class (therapeutic category). All ATC codes corresponding to a medication will be summarized, and patients will be counted once in each ATC category (anatomical or therapeutic) linked to the medication. Therefore, patients may be counted several times for the same medication.

The table for prior and concomitant medications will be sorted by decreasing frequency of ATC followed by all other therapeutic classes based on the overall incidence across all dose levels (i.e., the all patients column). In case of equal frequency regarding ATCs, alphabetical order will be used.

#### *Pre-medications*

Number (%) of patients with pre-medications (antihistamine, corticosteroids, h2 blocker, and acetaminophen) will be summarized by each administration until 7 and more than 7.

### 2.4.3 Extent of investigational medicinal product exposure and compliance

The extent of IMP exposure will be assessed and summarized by dose level cohort within the all treated population ([Section 2.3.1](#)).

The dose information will be assessed by the following variables.

- Number of cycles started
- Duration of isatuximab exposure (or time on-treatment) in weeks: defined as  $\{\min(\text{date of last dose of isatuximab} + X \text{ days, date of death}) - \text{first dose date}\} / 7$  (X equals to 7 in cycle 1 and 14 in the subsequent cycle). The theoretical duration of a cycle is 28 days
- Actual dose in mg/kg: for a given cycle and day of administration, the actual dose in mg/kg corresponds to the actual dose in mg administered at this time point divided by the actual body weight as measured at each time point
- Cumulative dose in mg/kg: the cumulative dose is the sum of all actual doses of isatuximab, expressed in mg/kg, given from first to last administration
- Actual dose intensity (ADI) in mg/kg/week: defined as the cumulative dose (in mg/kg) divided the duration of isatuximab exposure (in weeks)
- Relative dose intensity (RDI) in %:  $100 \times \text{ADI (mg/kg/week)} / \text{Planned Dose Intensity (mg/kg/week)}$

Planned dose intensities corresponds to the planned dose (mg/kg) received at Day 1 of cycle 1, multiplied by the theoretical total number of doses during the started cycles (count 2 for Q2W and 4 for QW), divided by the theoretical cycle duration expressed in weeks (i.e., 4 weeks), regardless of dose/schedule changes (as defined in the protocol section 6.5). ADI and RDI will be calculated separately in cycle 1 and subsequent cycles respectively, due to the difference of administration interval.

Total number of cycles started, number of cycles started by patients as a quantitative variable and by category (i.e., number [%] of patients receiving at least 1 cycle, at least 2 cycles...), duration of isatuximab exposure, cumulative dose, ADI, RDI, and RDI by category (< 80%, [80 - 105%),  $\geq 105\%$ ) will be summarized by descriptive statistics.

The following variables will be computed to describe dose delays and interruption:

- Cycle delayed is defined as follows:
  - A cycle is deemed as delayed if the start date of the current cycle - 28 - start date of the previous cycle is  $> 3$  days. Cycle delay is not defined for the first cycle.
- Infusion delay: within cycle 1, an infusion is deemed to be delayed if start date of the current administration - start date of previous administration - the theoretical duration (which is 7 days) is  $\geq 3$  days. For subsequent cycles ( $\geq$ cycle 2), an infusion is deemed to be delayed if start date of the current administration - start date of previous administration - the theoretical duration (which is 14 days) is  $\geq 4$  days
- Dose interruption: A dose will be considered to be interrupted if the isatuximab administration is temporarily stopped during an infusion and then restarted (typically in case of Grade 2 IARs).
- Dose reduction: although not allowed in the study protocol, potential dose reductions will be screened and reported in the clinical study report. The first administration will not be counted as a dose reduction. For the second and subsequent isatuximab administrations,

dose reduction will be determined using the dose level intervals provided in [Table 5](#), by comparing the current dose level to the previous dose level. If the current dose level is not within the same dose level interval as the previous dose level, then the current dose level is considered reduced.

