### 2.4.3 Extent of investigational medicinal product exposure and compliance

The extent of IMP exposure will be assessed and summarized within the all treated population (Section 2.3.1).

The dose information will be assessed by the following variables.

- Number of cycles started
- Duration of isatuximab exposure (or time on-treatment) in weeks is defined depending on the isatuximab administration schedule as follows:
  - If treatment is discontinued at a cycle with QW isatuximab administration: [date of last dose of isatuximab + 7 days – date of first dose of isatuximab] / 7.
  - If treatment is discontinued at a cycle with Q2W isatuximab administration: [date of last dose of isatuximab + 14 days – date of first dose of isatuximab] / 7.
- Actual dose in mg/kg: for a given cycle and day of administration, the actual dose in mg/kg corresponds to the actual dose in mg administered at this time point divided by the actual body weight as measured at each time point
- Cumulative dose in mg/kg: the cumulative dose is the sum of all actual doses of isatuximab, expressed in mg/kg, given from first to last administration
- Actual dose intensity (ADI) in mg/kg/week: defined as the cumulative dose (in mg/kg) divided the duration of isatuximab exposure (in weeks)
- Relative dose intensity (RDI) in %:  $100 \times \text{ADI (mg/kg/week)} / \text{Planned Dose Intensity (mg/kg/week)}$

Planned dose intensities corresponds to the planned dose (mg/kg) received at Day 1 of cycle 1, multiplied by the theoretical total number of doses during the started cycles (count 2 for Q2W and 4 for QW), divided by the theoretical cycle duration expressed in weeks (i.e., 4 weeks), regardless of dose/schedule changes (as defined in the protocol section 6.5). ADI and RDI will be calculated separately in cycle 1 and subsequent cycles respectively, due to the difference of administration interval.

Total number of cycles started, number of cycles started by patients as a quantitative variable and by category (i.e., number [%] of patients receiving at least 1 cycle, at least 2 cycles...), duration of isatuximab exposure, cumulative dose, ADI, RDI, and RDI by category (< 80%, [80 - 105%],  $\geq 105\%$ ) will be summarized by descriptive statistics.

The following variables will be computed to describe dose delays and interruption:

- Cycle delayed is defined as follows:

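### Phase 1 SAP 2.4.3 ends exposure at death and uses that duration as the dose-intensity denominator, so an on-schedule patient who dies within the last dosing interval gets a relative dose intensity above 100%

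*SAP*

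**What the plan says.** Section 2.4.3 of the Phase 1 SAP builds RDI in three steps.

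- **Exposure duration.** It is introduced with "Duration of isatuximab exposure (or time on-treatment) in weeks: defined as" and runs from the first dose to the earlier of two dates: the last dose plus X days, or death. The death term is the second argument of the minimum ("days, date of death"). On X: "X equals to 7 in cycle 1 and 14 in the subsequent cycle".
- **Actual dose intensity (ADI).** "Actual dose intensity (ADI) in mg/kg/week: defined as the cumulative dose (in mg/kg) divided the duration of isatuximab exposure (in weeks".
- **RDI.** ADI as a percentage of planned dose intensity. Planned intensity is the planned dose times the "theoretical total number of doses during the started cycles (count 2 for Q2W and 4 for QW), divided by the theoretical cycle duration" in weeks, that is, 4. It has no death term.

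The section adds: "ADI and RDI will be calculated separately in cycle 1 and subsequent cycles respectively, due to the difference of administration interval". RDI is summarised descriptively and in three categories: below 80%, 80% to below 105%, and 105% or more. No exception is made for patients who die.

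Two other places define the duration, both without a death term. Phase 2 SAP 2.4.3 uses the last dose plus 7 days for weekly dosing and plus 14 days for two-weekly dosing; the latter rule begins "If treatment is discontinued at a cycle with Q2W isatuximab administration". Protocol 13.4.2 uses Day 1 of the last cycle minus the first dose date plus 28 days. The change table in Phase 1 SAP 1.6 records that the exposure summary was revised to harmonise with other studies, but does not explain the death term.

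**The concern.** Ending time on treatment at death is reasonable in itself. The difficulty is using the same quantity as the denominator of a rate. The rule credits each dose with the 7 or 14 days that follow it. If the patient dies inside the last interval, the dose stays whole in the numerator and part of its interval leaves the denominator. Planned intensity stays at its full value, so the ratio rises.

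Protocol 13.4.2 presents RDI as a measure of whether the schedule is feasible. Under this rule an early death appears as more drug than planned and can fall in the 105%-or-more category. Phase 1 reports by dose-level cohort, and protocol 6.2.2 sets 3 to 6 patients per cohort, so one such value can pull the cohort mean and maximum. Phase 1 SAP 2.4.5.2 tabulates on-treatment deaths and deaths within 60 days of the first dose, so such deaths are contemplated.

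**Working it through.** The documents state no RDI value, so there is no figure to reproduce. The formulas can be calibrated on a patient who does not die.

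**Inputs (Phase 1 SAP 2.4.3).** Dose 20 mg/kg; the dose cancels, so 10 mg/kg gives the same RDI. X is 7 or 14 days. Planned intensity in Cycle 1 is 20 × 4 / 4 = 20 mg/kg/week. With one started later cycle it is 20 × 2 / 4 = 10 mg/kg/week.

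**Formula.** For n full, on-schedule doses and death t days after the last dose, with t no greater than X:

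- duration = ((n − 1)X + t) / 7 weeks
- ADI = 20n / duration
- RDI = 100 × ADI / planned intensity

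**Calibration.** Four Cycle 1 doses and survival to day 7 after the last give duration (21 + 7)/7 = 4 weeks, ADI 80/4 = 20 and RDI 100%. The formula is right until the death term operates.

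**Cycle 1, death 3 days after the last dose.** Here RDI reduces to 7n / (7(n − 1) + 3).

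| Doses | Calculation | RDI |
|---|---|---|
| 1 | 7/3 | 233% |
| 2 | 14/10 | 140% |
| 3 | 21/17 | 124% |
| 4 | 28/24 | 117% |

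Death on the day of the first dose gives duration 0, so ADI and RDI are undefined. Death 7 or more days after the last dose gives 100%.

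**Effect on a cohort.** With the other patients at 100%, one value of 233.3% gives a mean of (100 + 100 + 233.3)/3 = 144% for three patients, or (500 + 233.3)/6 = 122% for six. The median is 100% in both.

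**Later cycles, death 3 days after the last dose.** If the later-cycle clock starts at the first Cycle 2 dose, one later dose gives 14/3 = 467% and two give 28/17 = 165%. Both fall in a single later cycle, so planned intensity is 10 on any reading.

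For three or more later doses the reading of planned intensity matters. Four doses give ADI = 80/(45/7) = 12.4 mg/kg/week. Against a per-cycle planned value of 10 the RDI is 124%. Taken literally, the text counts doses over all started cycles and divides by a single 4 weeks. Two later cycles then give a planned value of 20 × 4 / 4 = 20 and an RDI of 62%.

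**Without the death term.** Using last dose plus X, each on-schedule example above returns 100%, provided planned intensity is taken per cycle where more than one later cycle has started. Under the duration rule in protocol 13.4.2, a patient who dies in Cycle 1 after one, two, three or four doses gets 25%, 50%, 75% or 100%, because the full 28 days are counted.

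**The case against.** The strongest reply is that this is a rare edge case in a descriptive table. It needs a death within 7 or 14 days of an infusion among 6 to 12 evaluable patients selected for a life expectancy of at least 3 months. The median is robust, cumulative dose and cycles started are summarised alongside RDI, dosing is listed, and every death is listed with its date. DLT assessment, dose escalation and ORR do not use RDI. All of this stands and limits the importance of the point, but it does not make the formula right.

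A second reply is that 100% as the correct value is a convention, since the protocol's own rule gives 25% for one Cycle 1 dose followed by death. That is also fair. The case rests on the SAP's own convention, which credits each dose with X days and which the death term then breaks. It also means that a fix must deal with the protocol's rule.

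The later-cycle figures are open to challenge because the Phase 1 SAP does not say how duration is split between Cycle 1 and later cycles. With the clock running from the first study dose, one later dose and death 3 days afterwards give a duration of (28 + 3)/7 = 4.43 weeks, an ADI of 20/4.43 = 4.5 and an RDI of 45%, not 467%. Starting the clock at Cycle 2 is the more natural reading, but it is an assumption.

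Two stronger readings are tempting and not supported:

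- A reader might infer that a Cohort 2 patient would receive two different RDIs, one from each SAP. The protocol synopsis and section 13.4 pool only efficacy across the phases, and nothing sends Cohort 2 exposure data through the Phase 2 formula. What remains is that RDIs in the two phases are not defined alike.
- A reader might infer that anyone with up to 16 later doses who dies at day 3 falls in the 105%-or-more category. That requires planned intensity per cycle. On the literal text, three or more later doses fall below 105%.

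**Conclusion.** The rule is wrong as written for dose intensity, and the consequence is minor. The Cycle 1 result follows directly from the text: RDI is above 100% whenever an on-schedule patient dies within 7 days of the last Cycle 1 dose. The excess is large after one dose and shrinks as doses accumulate. The 467% and 165% for later cycles hold only if the clock starts at the first Cycle 2 dose. Any figure for three or more later doses also needs planned intensity taken per cycle, which is not what the text literally says.

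The documents give no expected number of such deaths. With 0 to 1 affected patient assumed in Phase 1, the effect ranges from nothing to one distorted value in one cohort's mean and maximum, or one undefined value if death falls on the first dosing day. No decision rule or efficacy analysis is affected.

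**What to change.** In Phase 1 SAP 2.4.3, keep the death cut for reported time on treatment if it is wanted. Define a separate denominator for ADI and RDI: (date of last dose + X days − first dose date) / 7, with no death term, as in Phase 2 SAP 2.4.3. State that this replaces the duration rule in protocol 13.4.2, so that the departure is on record.

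In the same edit, say where the later-cycle clock starts and whether planned intensity is per cycle or summed over started cycles. Both are needed before any later-cycle RDI is determinate.

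The denominator change costs one line of SAP text and one programming change; the two clarifications need a sentence each. No new data are needed.

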**Table 5 – Dose reduction criteria**

Actual dose level	Dose level interval
Dose level 1 (10 mg/kg)	>0 mg/kg and $\leq$ 15 mg/kg
Dose level 2 (20 mg/kg)	>15 mg/kg and $\leq$ 25 mg/kg

- Infusion not completed: patients who received less than 90% of the planned dose at an infusion.

Dose modification will be analyzed at the patient, cycle, and total number of isatuximab administration levels as follows:

- Patient level
  - Number of patients
  - Number (%) of patients with at least 1 dose reduction
  - Number (%) of patients with at least 1 infusion interrupted
  - Number (%) of patients with at least 2 infusion interrupted
  - Number of patients who could have a cycle delayed (patients who received  $\geq$ 2 cycles, used for % calculation in this section):
    - Number (%) of patients with at least 1 cycle delayed
      - Number (%) of patients with a maximum cycle delayed between 4 and 7 days
      - Number (%) of patients with a maximum cycle delayed  $>$  7 days
    - Number of patients who could have an infusion delay (patients who received  $\geq$ 2 infusions, used for % calculation in this section).
      - Number (%) of patients with at least 1 infusion delay.
- Cycle level
  - Number of cycles administered (used for % calculation for this level)
  - Number (%) of cycles delayed
    - Number (%) of cycles with delay between 4 and 7 days
    - Number (%) of cycles with delay on  $>$  7 days
- Total number of isatuximab administration level
  - Total number of isatuximab administration (used for % calculation for this level)
  - Number (%) of isatuximab administration interrupted

- Number (%) of isatuximab infusions interrupted more than once
- Number of infusion interrupted at (with % calculated using the total number of infusions interrupted): 1st infusion, 2nd infusion, subsequent infusions.
- Time from infusion start to first interruption in minutes (quantitative (descriptive statistics) and qualitative: 5<, 5-10, 11-30, 31-40, 41-50, 51-60, 61-90, 91-120, >120), missing.
- Number (%) of infusions not completed (patients who received less than 90% of the planned dose)

Duration of infusion is defined as the time from the start (date/time) of infusion to the end (date/time) of infusion. It will be summarized with descriptive statistics for first and subsequent infusions. A listing of dosing data will be provided and include the following variables, number of cycles started, cycle-day, start date, cycle delayed, actual dose in mg/kg, dose interruption, dose reduced and dose not complete.

#### **2.4.4 Analyses of efficacy endpoints**

BOR will be summarized.

A listing of best percent change in % plasma cell in bone marrow biopsy will be provided and will include the following variables: measurable paraprotein at baseline, best percent change in paraprotein, BOR, baseline plasma cells count, best post baseline percent change in plasma cells count (only for CR confirmation) and MRD.

#### **2.4.5 Analyses of safety data**

The summary of safety results will be presented by dose level cohort.

##### ***General common rules***

All safety analyses will be performed on the safety population as defined in [Section 2.3.1](#). Unless otherwise specified, the baseline value is defined as the last available value before the first isatuximab administration.

##### **2.4.5.1 Analyses of adverse events**

###### ***Generalities***

The primary focus of adverse event reporting will be on treatment-emergent adverse events. Pre-treatment and post-treatment adverse events will be described separately.

If an adverse event date/time of onset (occurrence, worsening, or becoming serious) is incomplete, the adverse event will be classified as pre-treatment, treatment-emergent, or post-treatment, according to the cycle number or visit of onset. The algorithm for imputing date of onset will be conservative and will classify an AE as treatment emergent unless there is definitive information to determine it is pretreatment or post-treatment. Details on classification of adverse events with missing or partial onset dates are provided in [Section 2.5](#).

The grade will be taken into account in the summary. For patients with multiple occurrences of the same event during the observation period, the maximum grade is used.

Sorting within tables ensures the same presentation for the set of all adverse events within the observation period (pre-treatment, treatment-emergent, and post-treatment). For that purpose, the table of all treatment-emergent adverse events presented by SOC and PT sorted by the internationally agreed SOC order and decreasing frequency of PTs within SOCs in the highest dose level cohort will define the presentation order for all other tables unless otherwise specified.

The following treatment-emergent adverse event summaries will be generated by dose level for the safety population.

- Overview of treatment-emergent adverse events, summarizing number (%) of patients with any
  - Treatment-emergent adverse event (TEAE)
  - Grade 3-5 TEAE
  - Drug-related TEAE
  - Grade 3-5 drug-related TEAE
  - Serious TEAE
  - Drug-related serious TEAE
  - TEAE leading to death
  - TEAE leading to permanent treatment discontinuation
  - Dose limiting toxicity
  - Infusion associated reaction (excluding symptoms)
  - Grade 3-5 infusion associated reaction (excluding symptoms)
- All TEAEs by primary SOC, HLT, HLT and PT, showing number (%) of patients with at least 1 treatment-emergent adverse event sorted by the SOC internationally agreed order. The other levels (HLT, HLT and PT) will be presented in alphabetical order.
- All TEAEs by grade, primary SOC, and PT, showing the number (%) of patients with at least 1 treatment-emergent adverse event by grade (i.e., all grade,  $\geq$  grade 3).
- All serious TEAEs by primary SOC and PT, showing the number (%) of patients with at least 1 serious treatment-emergent adverse event.

- All TEAEs related to isatuximab, by primary SOC and PT, showing the number (%) of patients with at least 1 treatment-emergent adverse event related to isatuximab.
- All serious TEAEs related to isatuximab, by primary SOC and PT, showing the number (%) of patients with at least 1 treatment-emergent serious adverse event related to isatuximab.
- All TEAEs leading to treatment discontinuation, by primary SOC and PT, showing the number (%) of patients.
- All TEAEs leading to dose delay or interrupted, by primary SOC and PT, showing the number (%) of patients.
- All TEAEs with a fatal outcome, by primary SOC and PT, showing the number (%) of patients.
- All treatment-emergent DLT by primary SOC and PT, showing the number (%) of patients.
- All treatment-emergent IAR by primary SOC and PT, showing the number (%) of patients.
- IAR-AESI (using the CMQ corresponding to the generic term of infusion related reaction reported by investigator as an AESI):
  - Analysis by patient: number of patients (used as denominator), worst grade by patient, number of episodes by patient (only 1 episode,  $\geq 1$  episode,  $\geq 2$  episodes, .... – an episode corresponds to a unique AE reference ID), first occurrence of IARs, patients with IAR at the first and/or subsequent isatuximab infusion, and number (%) of patients with at least 2 episodes of IARs at the same infusion
  - Analysis by infusion: number of infusions (used as denominator), worst grade by infusion (a patient can have several IAR episodes at the same infusion).
  - Analysis by episode: number of episode (used as denominator), proportion of IARs occurring at each infusion, IAR duration, and day of onset
- IAR-AESI including symptoms as reported by investigator
  - Summary of IAR-AESI by SOC and PT
  - Listing of IAR-AESI

All AEs, AEs related to isatuximab, DLTs, IARs, respiratory AE, neutropenic complications, SAEs, and AEs leading to permanent treatment discontinuation are listed separately.

